9.2.2 Reporting Procedures for Serious Adverse Events

The investigator is responsible for ensuring that all serious adverse events observed by the investigator or reported by the subject that occur after signing of the informed consent through 30 days after last dose of IP (for subjects who have sustained platelet responses and never resume IP after sustained response during the trial); or the later of the EOT and EOS visits, are recorded in the subject’s medical record and are submitted

Product: Romiplostim
Protocol Number: 20101221
Date: 15 August 2014

Page 44 of 69

to Amgen. All serious adverse events must be submitted to Amgen within 24 hours following the investigator's knowledge of the event via the applicable CRF.

After the protocol-required reporting period defined above, the investigator does not need to actively monitor subjects for serious adverse events. However, if the investigator becomes aware of a serious adverse event after this protocol-required reporting period, the investigator will report the event to Amgen within 24 hours following the investigator's knowledge of the event. Serious adverse events reported outside of the protocol-required reporting period will be captured within the safety database as clinical trial cases for the purposes of expedited reporting.

If the electronic data capture (EDC) system is unavailable to the site staff to report the Serious Adverse Event, the information is to be reported to Amgen via an electronic Serious Adverse Event (eSAE) Contingency Report Form within 24 hours of the Investigator's knowledge of the event. See [Appendix A](#) for a sample of the Serious Adverse Event Worksheet/electronic Serious Adverse Event Contingency Report Form. For EDC studies where the first notification of a Serious Adverse Event is reported to Amgen via the eSerious Adverse Event Contingency Report Form, the data must be entered into the EDC system when the system is again available

The investigator must assess whether the serious adverse event is possibly related to any study-mandated activity or procedure. This relationship is indicated by a "yes" or "no" response to the question: "Is there a reasonable possibility that the event may have been caused by a study activity/procedure"?

The investigator is expected to follow reported serious adverse events until stabilization or reversibility.

New information relating to a previously reported serious adverse event must be submitted to Amgen. All new information for serious adverse events must be sent to Amgen within 24 hours following knowledge of the new information. The investigator may be asked to provide additional follow-up information, which may include a discharge summary or extracts from the medical record. Information provided about the serious adverse event must be consistent with that recorded on the applicable CRF (eg, Adverse Event Summary CRF).

If a subject is permanently withdrawn from the study because of a serious adverse event, this information must be submitted to Amgen.

Product: Romiplostim
Protocol Number: 20101221
Date: 15 August 2014

Page 45 of 69

Amgen will report serious adverse events and/or suspected unexpected serious adverse reactions as required to regulatory authorities, investigators/institutions, and IRBs/IECs in compliance with all reporting requirements according to local regulations and good clinical practice.

The investigator should notify the appropriate IRB/IEC of serious adverse events occurring at the site and other adverse event reports received from Amgen, in accordance with local procedures and statutes.

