3.1.1 Subjects With an Onset of Sustained Platelet Response

During the treatment period, romiplostim doses will be adjusted as outlined in [Table 1](#). Subjects who dose reduce romiplostim such that they no longer require treatment with romiplostim, no longer require ITP medications (concomitant or rescue), and have an onset of a sustained platelet response (defined as a consecutive platelet counts $\geq 50 \times 10^9/L$) will be monitored for at least 6 months beginning with the first platelet count $\geq 50 \times 10^9/L$. Subjects whose platelet count remains $\geq 50 \times 10^9/L$ in the absence of any medications for ITP for at least 6 months will then be followed every 12 weeks for the duration of the 36-month treatment period.

If during the 36-month treatment period the platelet count subsequently falls below $< 50 \times 10^9/L$, treatment with romiplostim at the initial starting dose may be resumed. Subsequent doses will be adjusted as shown in [Table 1](#). Clinic visits will be resumed per the Schedule of Assessments ([Table 2](#)).

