7.1 Schedule of Assessments

The Schedule of Assessments is found in [Table 2](#) below.

Table 2. Schedule of Assessments

Procedures	Screening	In Clinic Dosing Period ^a	Romiplostim Treatment Period (up to 36-months) ^b			End Of Treatment Visit	End of Study Visit
	- 4 Weeks	Week 1 to Week 8	Weekly	Every 4 Weeks	Every 12 Weeks		
Informed consent	X						
Confirmation of primary ITP diagnosis	X						
ITP/medical history	X						
Physical exam	X				X	X	
Vital signs	X				X	X	
Weight	X				X		
Central lab CBC with differential	X	X ^c		X ^b		X	
Central lab blood (serum) chemistry	X				X	X	
Local lab platelet counts	X	X	X ^{b,d}			X	X
Local lab peripheral blood smear		X ^c		X ^b		X	
Pregnancy test	X				X ^f	X ^f	
Concomitant /rescue medications	X	X	X	X	X	X	X
Adverse event reporting		X	X	X	X	X	
Serious adverse events	X	X	X	X	X	X	X
Antibody sample ^e		Day 1 (before first dose)			W12, W52 and every 24 weeks thereafter	X	
Romiplostim dosing		X	X				

ITP = immune thrombocytopenia; CBC = complete blood counts

- ^a Week 1 to Week 8. All subjects will return to the clinic for weekly dosing of romiplostim, platelet counts by a local laboratory, recording of concomitant/rescue medications, and adverse event reporting.
- ^b Subjects who complete 6 months of sustained platelet response (platelet count $\geq 50 \times 10^9/L$ in the absence of romiplostim or any ITP medications) will have assessments every 12 weeks for the duration of the 36-month treatment period.
- ^c Central CBC with differential and local lab peripheral blood smears are to be performed every 4 weeks, including pre-dose at week 1. Screening laboratory studies may be used in lieu of the pre-treatment day 1 week 1 laboratory tests if performed within 10 days prior to the first dose. Bone marrow biopsy suggested if abnormalities detected.
- ^d For subjects who establish a stable dose of romiplostim and are self-administering, have the injection administered by a caregiver, or meet this criterion but still prefer to come to the clinic for romiplostim administration, platelet counts will be monitored every 4 weeks.
- ^e For subjects who test positive for antibodies, see [Section 7.1.3](#). Antibody sampling during romiplostim treatment is only conducted if subject is receiving study drug.
- ^f Local lab urine or serum pregnancy test for female subjects of child-bearing potential (defined as having first menses)

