If the subject has maintained a sustained platelet response, subsequent visits and procedures including the platelet counts, CBC, and peripheral blood smears will be performed every 12 weeks for the duration of the 36-month treatment period. If the subject's platelet counts fall to $< 50 \times 10^9/L$ and treatment with romiplostim is resumed, the visit schedule will revert to weekly platelet counts, and CBC with peripheral blood smear evaluations every 4 weeks. The visit assessment weeks and procedures resume counting from first dose of romiplostim after enrollment.

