7.7 End of Treatment Visit (EOT)

All subjects will complete an EOT visit. For subjects who complete the 36-month treatment period and who have been off romiplostim and other medications for ITP (concomitant or rescue) for 4 weeks or more, the EOT visit will be the final study visit and will occur after the completion of the 36-month treatment period. For subjects ending the 36-month treatment period for non-response or other reasons while still receiving romiplostim, this visit will be 1 week after the last administration of romiplostim.

The following assessments will be completed at the EOT visit:

- physical exam, including vital signs
- documentation of concomitant and rescue medications
- adverse event reporting
- central lab CBC with differential and blood chemistry
- local lab platelet counts
- collection of blood samples for anti-romiplostim antibodies
- local lab peripheral blood smear
- local lab urine or serum pregnancy test for female subjects of child-bearing potential (defined as having first menses)

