9.2 Reporting of Adverse Events

9.2.1 Reporting Procedures for Adverse Events That do not Meet Serious Criteria

The investigator is responsible for ensuring that all adverse events observed by the investigator or reported by the subject that occur after first dose of investigational product through the end of treatment period are reported using the applicable eCRF (eg, Adverse Event Summary CRF).

Because all subjects who enter the study will be diagnosed with ITP according to the ASH guidelines, ITP should not be reported as an adverse event during the conduct of the study.

The investigator must assign the following adverse event attributes:

- adverse event diagnosis or syndrome(s), if known (if not known, signs or symptoms)
- dates of onset and resolution (if resolved)

- severity
- assessment of relatedness to romiplostim
- action taken

The adverse event severity grading scale used will be the Common Terminology Criteria for Adverse Events (CTCAE) version 3.0 grading scale. The severity grading scale used in this study is described in [Appendix A](#).

The investigator must assess whether the adverse event is possibly related to the romiplostim. This relationship is indicated by a “yes” or “no” response to the question: Is there a reasonable possibility that the event may have been caused by the romiplostim?

The investigator must assess whether the adverse event is possibly related to any study-mandated activity (eg, administration of investigational product, protocol-required therapies, device(s) and/or procedure (including any screening procedure(s))). This relationship is indicated by a “yes” or “no” response to the question: “Is there a reasonable possibility that the event may have been caused by a study activity (eg, administration of investigational product, protocol-required therapies, device(s)), and/or procedure?”

The investigator is responsible for reviewing laboratory test results and determining whether an abnormal value in an individual study subject represents a clinically significant change from the subject’s baseline values. In general, abnormal laboratory findings without clinical significance (based on the investigator’s judgment) are not to be recorded as adverse events. However, laboratory value changes that require treatment or adjustment in current therapy are considered adverse events. Where applicable, clinical sequelae (not the laboratory abnormality) are to be recorded as the adverse event.

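### For children who stop romiplostim in sustained response, the protocol gives conflicting SAE collection windows and neither document fits the SAE-rate denominator to either one

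*Protocol*

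**What the plan says.** **Collection.** Protocol 9.2.2 sets two end-points for required SAE reporting. For one group it runs "through 30 days after last dose of IP (for subjects who have sustained platelet responses and never resume IP" later in the trial. For the rest it runs to the later of the EOT and EOS visits. After the required period, "the investigator does not need to actively monitor subjects for serious adverse events". SAEs the investigator does learn of must still be reported, and they "will be captured within the safety database as clinical trial cases for the purposes of expedited reporting".

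**Follow-up of the same children.** They stay in the study. Protocol 3.1.1 says that, after at least six months of monitoring, they "will then be followed every 12 weeks for the duration of the 36-month treatment period". Section 7.6 says that "subsequent visits and procedures including the platelet counts, CBC, and peripheral blood smears will be performed every 12 weeks", and footnote b of Table 2 (Section 7.1) that they "will have assessments every 12 weeks for the duration of the 36-month treatment period". For those who complete while off ITP medication, Section 7.7 says "the EOT visit will be the final study visit and will occur after the completion of the 36-month treatment period".

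**Other collection rules.** Table 2 marks SAEs in every column, including the 12-weekly and EOT columns. Section 9.2.1, headed as covering events that do not meet serious criteria, requires adverse events "that occur after first dose of investigational product through the end of treatment period are reported".

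**Rates.** Protocol 10.3.2.2 and SAP 10.6.1 define the exposure-adjusted rate as the number of events divided by the time subjects were under observation, with SAEs as a listed category. SAP 4.3 calculates duration-adjusted rates over the whole study and by six-month period. Protocol 10.3.2.2 and SAP 10.6.1 treat the by-period rates as optional.

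**The concern.** There are two problems, and they compound.

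First, the protocol does not give sites one answer on when SAE collection ends for these children. Under 9.2.2 it ends 30 days after the last dose; under Table 2 it continues to EOT. If 9.2.1 is confined to non-serious events, as its heading says, then after day 30 a mild event must be recorded while a serious one need not be sought. The 9.2.2 condition also cannot be applied when it is needed: whether a child never resumes romiplostim is not known at day 30, because 3.1.1 and 6.2.1 provide for resumption at any time in the 36 months.

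Second, the rate definition has no cut that matches the 30-day window. A numerator collected over one span and a denominator counted over a longer one give a rate that is too low. The unmatched time falls late in follow-up, so any six-monthly SAE rates could decline because of collection rather than safety. Long-term safety is a stated secondary objective, so these rates matter to what the study reports.

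**Working it through.** **No figure to reproduce.** The documents give no SAE rate, no expected number of children stopping in sustained response and no time of stopping. What can be checked is whether the windows match, and how large a mismatch would be on stated assumptions.

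**1. The windows side by side, for a child who stops for good at month t0**

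| Source | What it governs | End |
|---|---|---|
| Protocol 9.2.2 | Required SAE collection | t0 + 30 days |
| Protocol Table 2 | Scheduled SAE collection | EOT, after month 36 |
| Protocol 9.2.1 | Adverse events (headed non-serious) | End of treatment period, a term the protocol uses for the full 36 months |
| Protocol 10.3.2.2, SAP 10.6.1 | Rate denominator | Time under observation, no end date given |
| SAP 6, treatment duration | Not tied to the rate | t0 + 7 days |

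The first row conflicts with the second. The denominator row matches the first only if a cut is added.

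**2. Four combinations**

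- Sites apply 9.2.2, denominator runs to month 36: mismatch, SAE rate too low.
- Sites follow Table 2, denominator runs to month 36: spans match, provided the late SAEs are tabulated.
- Sites apply 9.2.2, denominator is SAP treatment duration: no dilution, because person-time ends 23 days (30 − 7) before the SAE window closes.
- Sites follow Table 2, denominator is SAP treatment duration: no dilution, but the numerator then needs its own cut.

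Only the first combination produces the downward bias.

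**3. Illustration of the first combination**

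Assumed, not from the documents: a share s = 20% stops for good at t0 = 12 months, and everyone is followed 36 months. From the documents: N = 200, a 30-day window and a 36-month treatment period. With 30.44 days per month, 30 days = 0.986 month.

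- Uncovered time per such child: 36 − 12 − 0.986 = 23.01 months.
- Share of all person-time: 0.20 × 23.01 / 36 = 12.8%.
- In child-years: 200 × 0.20 × 23.01 / 12 = 76.7 of 600.
- By six-month period: 0% to month 12; 0.20 × (6 − 0.986) / 6 = 16.7% in months 12–18; 20% in each later period.

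With a constant underlying SAE rate and no late SAE tabulated, the reported overall rate would be 1 − 0.128 = 0.872 of the rate on covered time. If half the late SAEs were tabulated, the shortfall would be 12.8 / 2 = 6.4%.

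**4. Range on other assumptions**

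- s = 5%, t0 = 24, all followed 36 months: 0.05 × 11.01 / 36 = 1.5%.
- s = 30%, t0 = 12, all followed 36 months: 0.30 × 23.01 / 36 = 19.2%.
- s = 30%, t0 = 12, other children averaging 24 months: 0.30 × 23.01 / (0.30 × 36 + 0.70 × 24) = 6.90 / 27.6 = 25.0%.

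The result follows the assumed share and timing almost directly. None of these figures is a bound.

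**The case against.** The strongest reply is that neither half of the mismatch is certain.

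- **Denominator.** Neither document says that off-drug follow-up counts. The rates are called exposure-adjusted or duration-adjusted, the events are treatment-emergent, and SAP 6 defines a treatment duration ending seven days after last dose. A reader might infer that off-drug time is definitely in the SAE denominator. The documents do not support that: it is the literal reading of the rate definition and of the whole-study span in SAP 4.3, but an on-treatment denominator remains open. Equally, SAP 6 is not tied to the rate, so it does not settle the matter the other way.
- **Collection.** A reader might also infer that SAE collection in fact stops at day 30. Table 2 exempts no one, and an investigator asking about adverse events at 12-weekly visits will usually hear of serious ones, which must then be reported. Because the never-resume condition cannot be verified at day 30, a cautious site would keep collecting. This stands, and could bring the gap close to zero. But practice could differ among about 50 centers, and the only destination 9.2.2 gives for late SAEs is the safety database. Neither document says whether they enter the rate tables.
- **Time trend.** An artefactual fall in six-monthly SAE rates should not be presumed. SAP 4.3 plans these rates, while SAP 10.6.1 and Protocol 10.3.2.2 make them optional.
- **The 30-day window itself.** It is close to the four-week EOS visit for subjects who end while on drug (Protocol 7.8), so it is not unreasonable in itself. The fault is that it disagrees with Table 2 and that no denominator is fitted to it.

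The study is also descriptive, with no hypothesis test, which limits the consequence to the reported safety rates.

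**Conclusion.** The inconsistency between 9.2.2 and Table 2, and its tension with 9.2.1, is in the text and needs resolving. So does the missing end date for the SAE denominator. The downward bias is conditional: it arises only if sites apply 9.2.2 and time under observation is taken to include off-drug follow-up. It then affects the overall SAE rate and, more strongly, the later periods if period rates are produced. SAE subject incidence is affected only through events that are missed.

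The size cannot be derived from the documents. The 12.8% illustration rests on an assumed 20% stopping for good at month 12, full 36-month follow-up, a constant SAE rate and no late SAE tabulated; other assumptions gave 1.5% to 25.0%. The primary endpoint and the sample size do not depend on any of this.

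**What to change.** **Preferred, at the next protocol amendment.** Reconcile 9.2.2 with 9.2.1 and Table 2 so that there is one stated SAE collection window for these children, expressed in terms a site can apply at the time. The cost is about one sentence, but it needs IRB/IEC approval (Protocol 12.1) at about 50 centers (Protocol 3.2), so it should be bundled with other changes. The visits are already scheduled.

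**Otherwise, in the SAP without an amendment.** State that, for children who stop in sustained response and do not resume, SAE person-time ends when required SAE collection ends (last dose plus 30 days), overall and in any period analysis. State also that later SAEs are listed separately and not counted in the rate. The cost is one rule and some person-time: in the illustration, 600 − 76.7 = 523.3 child-years remain. This makes numerator and denominator match, but it leaves the conflicting instructions to sites in place and recovers no missed event.

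Either way, the rule should be settled before SAE rates are produced for the interim analyses, which are planned at least annually.

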9.3 Pregnancy and Lactation Reporting

If a pregnancy occurs in a female subject, or female partner of a male subject, while the subject is taking protocol-required therapies report the pregnancy to Amgen as specified below.

In addition to reporting any pregnancies occurring during the study, investigators should monitor for pregnancies that occur after the last dose of protocol-required therapies through 1 month after the last dose of romiplostim.

The pregnancy should be reported to Amgen's global Pregnancy Surveillance Program within 24 hours of the investigator's knowledge of the event of a pregnancy. Report a pregnancy on the Pregnancy Notification Worksheet ([Appendix C](#)). The Pregnancy Surveillance Program (PSP) will seek to follow the pregnant woman throughout her pregnancy and her baby up to 12 months after birth.

If a lactation case occurs while the female subject is taking protocol-required therapies report the lactation case to Amgen as specified below.

In addition to reporting a lactation case during the study, investigators should monitor for lactation cases that occur after the last dose of protocol-required therapies through 1 month after the end of the dose of romiplostim.

Any lactation case should be reported to Amgen's global Lactation Surveillance Program (LSP) within 24 hours of the investigator's knowledge of event. Report a lactation case on the Lactation Notification Worksheet ([Appendix D](#)).

10. STATISTICAL CONSIDERATIONS

The statistical analysis of this open-label study will be descriptive in nature only. No hypothesis testing is planned. Categorical data will be presented in the form of number and percentage. Continuous data will be provided with the descriptive statistics

Product: Romiplostim
Protocol Number: 20101221
Date: 15 August 2014

Page 46 of 69

(n, mean, standard deviation, median, Q1 [25th percentile], Q3 [75th percentile], minimum, and maximum).

10.1 Study Endpoints, Subsets, and Covariates

10.1.1 Study Endpoints

Primary Endpoint:

- The percentage of time with a platelet count of $\geq 50 \times 10^9/L$ starting from week 2 in the first 6 months of the treatment period without rescue medication use within the past 4 weeks

Secondary Endpoints:

- The percentage of time with a platelet count of $\geq 50 \times 10^9/L$ starting from week 2 until the end of the treatment period without rescue medication use within the past 4 weeks
- The percentage of time with an increase in platelet count $\geq 20 \times 10^9/L$ above baseline starting from week 2 until the end of the treatment period without rescue medication use in the past 4 weeks.
- Subject incidence of rescue ITP medications used
- The incidence of anti-romiplostim neutralizing antibodies and cross reactive antibodies to TPO at any time during the study
- The incidence of adverse events, including clinically significant changes in laboratory values

Exploratory Endpoints:

- The subject incidence with a sustained platelet count of $\geq 50 \times 10^9/L$ for 6 months or greater without the use of any ITP medications (concomitant, rescue, or romiplostim)
- The incidence of splenectomy during the treatment period for subjects entering the study pre-splenectomy
- The subject incidence of romiplostim self-administration

